7.2 Handling of Dropouts or Missing Data

For the primary analysis of the primary efficacy endpoint, subjects with missing data at Week 8 or Week 26 for the Double-blind Acute Phase or Double-blind Maintenance Phase, respectively, will be assumed not to have had a clinical response and will be considered treatment failures.

Sensitivity analyses to examine the handling of missing data for the primary efficacy endpoint include complete-case analysis and last observation carried forward. These are described in Section 7.7.

7.3 Interim Analysis and Data Monitoring

A safety review team will review safety data twice a year according to the Data Review Plan.

There is no interim efficacy analysis planned for this study. An independent Data Monitoring Committee (DMC) will monitor safety data generated by the study at regular intervals for the duration of the study. Their role is to protect the interests of subjects in the study and of future subjects who may enroll, by reviewing the accumulating safety and tolerability data generated in this study. DMC meetings will be held on 3 occasions—the first time after one-fourth of the targeted sample size is evaluable for analysis, the second time after two-fourth are evaluable, and third time after three-fourth are evaluable. The data provided to the DMC will not be considered ‘clean’ until the database is locked. Data will be provided to the DMC by an independent statistical reporting group not assigned to the project.

Further details regarding the DMC and meeting frequency can be found in the DMC charter. The DMC charter will define the primary responsibilities of the DMC, guide its activities, its relationship with other trial components, its membership, and the purpose and timing of its meetings. It will provide the procedures for ensuring confidentiality, formal communication, an outline of the content of the Open and Closed Reports that will be provided to the DMC.

7.4 Multicenter Studies

Data from all centers that participate in this protocol will be combined so that an adequate number of subjects will be available for analysis.

7.5 Multiple Comparisons/Multiplicity

This is an estimation study intended to provide estimates of clinical response for 2 doses (low and high) across a range of weight groups and not powered to detect differences between treatment groups. No adjustment for multiplicity will be performed.

7.6 Examination of Subgroups and Interactions

As indicated for each subgroup analysis, efficacy endpoints will be summarized by study phase (Double-blind Acute Phase, Open-label Acute Phase, and Double-blind Maintenance Phase) using the appropriate Safety Analysis Set for that phase.

7.6.1 Weight Group

The primary efficacy endpoint will be summarized for each study phase by weight group (18 to \leq 23kg, >23 to \leq 35kg, >35 to \leq 50kg and >50 to \leq 90kg).

7.6.2 Prior Response Status

The primary and secondary efficacy endpoints will be summarized for the Double-blind Maintenance Phase by prior response status (entered Maintenance Phase directly, responder at Week 8 in Double-blind Acute Phase, responder at Week 8 in Open-label Acute Phase). This analysis will provide information on the durability of response with respect to the prior treatment with either MMX or other 5-ASA treatment.

In addition, the primary and secondary efficacy endpoints will be summarized for the Double-blind Maintenance Phase by prior response status (entered Maintenance Phase directly, responder at Week 8 in Double-blind Acute Phase, responder at Week 8 in Open-label Acute Phase) and prior treatment (low-dose MMX, high-dose MMX, and 5-ASA by medication preferred term). This analysis will provide information on the durability of response with respect to the prior MMX dose group or other 5-ASA treatments by preferred term.

The number (n, %) of subjects with a clinical response at Week 26 and difference between treatment arms for each stratum, together with the 95% CI (2-sided), and associated p-value will be presented.

7.7 Sensitivity Analyses

7.7.1 Sensitivity Analyses of the Primary Endpoint

The following sensitivity analyses will be performed for both the Double-blind Acute and Double-blind Maintenance Phase primary endpoint:

- A modified clinical response, defined as partial UC-DAI \leq 1 with rectal bleeding=0 and stool frequency \leq 1 will be analyzed in a similar way to the primary endpoint analysis in order to investigate the effect of removing the PGA component from the responder definition.

- A modified clinical response, defined as partial UC-DAI \leq 1 with rectal bleeding=0 and stool frequency=0, and PGA=0 will be analyzed in a similar way to the primary endpoint to support extrapolation to adult efficacy.
- A complete-case analysis (where subjects who withdraw early from the study are excluded) will be performed in a similar way to the primary endpoint analysis.
- A last observation carried forward analysis (LOCF), using data from the final on-treatment assessment (FoTA) for the appropriate phase, will be performed in a similar way to the primary endpoint analysis. Specifically, the values of the individual components of the partial UC-DAI (rectal bleeding, stool frequency and PGA scores) will be imputed using the last observation carried forward (LOCF) method.
- Logistic modeling will be conducted to investigate the effect of doses in mg/kg on the clinical response in the Double-blind Acute and Double-blind Maintenance Phases. The logistic regression model will adjust for doses in mg/kg, sex, and age. For the Double-blind Maintenance Phase primary endpoint, the logistic regression model will also adjust for Week 8 responder status.

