6.2.2 Allocation of Subjects to Treatment

This study includes 2 double-blind phases with low and high-dose MMX mesalamine/mesalazine. The actual double-blind treatment given to individual subjects is determined by a randomization schedule stratified by weight group. Randomization will be a 1:1 ratio between low and high doses.

Subject numbers are assigned to all subjects as they consent to take part in the study. Within each site (numbered uniquely within a protocol), the subject number is assigned to subjects according to the sequence of presentation for study participation.

The randomization number represents a unique number corresponding to investigational product allocated to the subject, once eligibility has been determined.

Individual subject doses in the Double-blind Acute Phase are automatically assigned by the IRT based on subject weight group at the Baseline Visit (Visit 2). If the subject is directly entering the Double-blind Maintenance Phase, individual doses are also automatically assigned by the IRT based on subject weight group at the Baseline Visit (Visit 2).

Individual subject open-label treatment is automatically assigned by the IRT and will be the high dose based on the subject's weight group at Visit 3.2 (Week 8/Withdrawal of the Double-blind Acute Phase).

Individual subject double-blind doses for subjects being re-randomized to the Double-blind Maintenance Phase after completion of treatment at Visit 3.2 (Week 8 of the Double-blind Acute Phase) or Visit 4.2 (Week 8 of the Open-label Acute Phase) are automatically assigned by the IRT based on subject weight group at the time of re-randomization.

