1.2 Background

This is a phase 3, multicenter, randomized, double blind study to determine the safety and efficacy of Multi Matrix System (MMX) mesalamine/mesalazine in pediatric subjects (aged 5-17 years) with mild to moderate ulcerative colitis (UC). This study is comprised of an 8-week Double-blind Acute Phase and a 26-week Double-blind Maintenance Phase. Each phase includes 2 arms, and subjects will be randomized to 1 of 2 doses (low or high) of MMX mesalamine/mesalazine (900-4800mg/day, given once daily) at the beginning of each phase. Randomization will be in a 1:1 ratio stratified by body weight group.

The data from this study will:

- Aid in selection of appropriate doses in the pediatric population
- Determine whether MMX mesalamine/mesalazine is safe and effective for use in children and adolescents (aged 5-17 years) with mild to moderate UC or who are in remission.

The study allows all subjects to receive active MMX mesalamine/mesalazine. The doses for the study were determined from pharmacokinetic modeling using data from the SPD476-112 study, a pharmacokinetic study in children and adolescents with mild to moderate UC.

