Subjects may enter the Double-blind Maintenance Phase directly following the Baseline Visit (Visit 2) if they have a partial UC-DAI ≤ 1 (with rectal bleeding=0 and stool frequency ≤ 1 and PGA=0) and with mucosal appearance (endoscopy score) = 0 or 1 at that visit.

MMX mesalamine/mesalazine is dosed once daily by mouth. The selection of doses in this study is based on an approximate average of 43mg/kg for the low dose and 85mg/kg for the high dose in the 3 lower weight groups (18 to ≤ 23 kg, > 23 to ≤ 35 kg and > 35 to ≤ 50 kg). These doses were selected based on standard of care dosing for other 5-ASA products in the pediatric population and pharmacokinetic dosing results. The dosing for the highest weight group (> 50 to ≤ 90 kg) is based on adult UC experience.

[figure not shown]
Minimum enrollment criteria have been agreed with FDA as follows, based on subject weight group:

Table 1: Minimally Required Number of Subjects per Weight Group

Weight Group	Low Dose (mg/day)	High Dose (mg/day)	Number of Subjects in Combined Low and High Dose ^a
18 to <23kg	900	1800	2
>23 to ≤35kg	1200	2400	12
>35 to ≤50kg	1800	3600	18
>50 to ≤90kg	2400	4800	36

^a Randomization will be stratified by weight group with the aim of creating balance between the 2 dose groups within a weight group

Figure 1: Study Design Flow Chart

PGA=Physician's Global Assessment; UC-DAI=Ulcerative Colitis Disease Activity Index.

^a Subjects with partial UC-DAI ≥ 2 (with a combined rectal bleeding and stool frequency score ≥ 1 and PGA=1 or 2) and with mucosal appearance (endoscopy score)=2 or 3.

^b Subjects with partial UC-DAI ≤ 1 (with rectal bleeding=0 and stool frequency ≤ 1 and PGA=0) and with mucosal appearance (endoscopy score)=0 or 1.

Notes: Solid boxes indicate study phases. Dashed ellipses indicate decision points.

Subjects will initially be randomized into either the 8-week Double-blind Acute Phase or the 26-week Double-blind Maintenance Phase based on partial UC-DAI and mucosal appearance scores. Subjects who do not achieve a clinical response or who have withdrawn from the Double-blind Acute Phase after a minimum of 2 weeks and, in the investigator's opinion, have not benefited from treatment in the Double-blind Acute Phase may enter the Open-label Phase. Subjects without a clinical response after completion of acute treatment in the Open-label Acute Phase must be withdrawn.

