3.3 Method of Assigning Subjects to Treatment Groups

This study includes 2 double-blind phases with low- and high-dose MMX mesalamine/mesalazine. The actual double-blind treatment given to individual subjects is determined by a randomization schedule stratified by weight group. Randomization will be a 1:1 ratio between low and high doses.

Subject numbers are assigned to all subjects as they consent to take part in the study. Within each site (numbered uniquely within a protocol), the subject number is assigned to subjects according to the sequence of presentation for study participation.

The randomization number represents a unique number corresponding to investigational product allocated to the subject, once eligibility has been determined.

Subjects eligible for either the Double-blind Acute or the Double-blind Maintenance Phase can be re-randomized if they initially failed randomization for the following reasons: incorrect use of IVRS, late or missing central laboratory or endoscopy results, or other reasons of this type as long as they meet inclusion and exclusion criteria. Re-randomization can only take place after consultation with the medical monitor.

Individual subject doses in the Double-blind Acute Phase are automatically assigned by the interactive response technology (IRT) based on subject weight group at the Baseline Visit (Visit 2). If the subject is directly entering the Double-blind Maintenance Phase, individual doses are also automatically assigned by the IRT based on subject weight group at the Baseline Visit (Visit 2).

Individual subject open-label treatment is automatically assigned by the IRT and will be the high dose based on the subject's weight group at Visit 3.2 (Week 8/Withdrawal of the Double-blind Acute Phase).

Individual subject double-blind doses for subjects being re-randomized to the Double-blind Maintenance Phase after completion of treatment at Visit 3.2 (Week 8 of the Double-blind Acute Phase) or Visit 4.2 (Week 8 of the Open-label Acute Phase) are automatically assigned by the IRT based on subject weight group at the time of re-randomization.

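### The mg/kg logistic model omits body weight, so its dose coefficient mixes the randomised dose with body size if response depends on weight given age and sex

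*SAP*

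**What the plan says.** SAP section 7.7.1 closes its list of sensitivity analyses with a dose-response model: "Logistic modeling will be conducted to investigate the effect of doses in mg/kg on the clinical response", in both double-blind phases. The covariates follow: "The logistic regression model will adjust for doses in mg/kg, sex, and age". For the Maintenance Phase, "the logistic regression model will also adjust for Week 8 responder status". Weight, weight group and randomised arm do not appear. Protocol section 9.8.2 announces the same model without naming covariates.

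Treatment is "determined by a randomization schedule stratified by weight group" (SAP section 3.3), and "Randomization will be a 1:1 ratio between low and high doses". Protocol section 6.2.3 sets one low and one high daily dose in mg for each of four weight bands, the high dose being twice the low. Section 7.1.1.3 keeps the dose unchanged within a phase. For children moving into the Maintenance Phase from an acute phase, doses "are automatically assigned by the IRT based on subject weight group at the time of re-randomization" (Protocol section 6.2.2).

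On the choice of doses, SAP section 3.1 states: "The selection of doses in this study is based on an approximate average of 43mg/kg for the low dose and 85mg/kg for the high dose". That applies to the three lighter bands; the heaviest band was dosed from adult experience. SAP section 1.2 gives as one aim of the study: "Aid in selection of appropriate doses in the pediatric population". Neither document says which weight measurement defines mg/kg in the model.

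**The concern.** Randomisation protects the low versus high contrast, not mg/kg. Within an arm and a band, mg/kg differs between two children only because their weights differ. Across bands, the heaviest children sit lower on the mg/kg scale because their band was dosed on another basis. A model with mg/kg but no weight term therefore credits to dose any association between body size and response that sex and age do not absorb.

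The study is described as an estimation study, so a shifted estimate is the harm to look at, more than a shifted p-value. The model has its own output table in each phase (14.2.1.2.6 and 14.2.1.2.15). Its scale is the one on which the doses for the three lighter bands were chosen, so it is likely to be read when paediatric doses are discussed.

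**Working it through.** **1. The plan's own figure.** Low dose divided by band-midpoint weight, for the three lighter bands (doses from Protocol section 6.2.3):

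- 900/20.5 = 43.9; 1200/29 = 41.4; 1800/42.5 = 42.4 mg/kg.
- Mean = 42.5 low; doubled, 85.1 high. This agrees with the stated 43 and 85.
- Heaviest band, same method: 2400/70 = 34.3 low and 68.6 high.

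**2. What moves mg/kg.** log(mg/kg) = log(low dose of the band) + log 2 if in the high arm − log(weight). Only the middle term is randomised. At the band edges:

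| Band (kg) | Low arm (mg/kg) | High arm (mg/kg) |
|---|---|---|
| 18–23 | 39.1–50.0 | 78.3–100.0 |
| 23–35 | 34.3–52.2 | 68.6–104.3 |
| 35–50 | 36.0–51.4 | 72.0–102.9 |
| 50–90 | 26.7–48.0 | 53.3–96.0 |

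Each arm spans about a two-fold range, set by weight and band. The arms do not overlap: the low arm tops out at 52.2 and the high arm starts at 53.3.

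**3. How much of the mg/kg variation is weight.** Assumptions: band mix 2:12:18:36 (the minimum numbers in SAP Table 1 used as proportions), uniform weights within bands, 1:1 allocation. The documents give no weight distribution, so the top of the heaviest band was varied.

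| | Top band to 90 kg | Top band to 70 kg |
|---|---|---|
| Share of mg/kg variance within arm | 22% | 10% |
| Same, after age and sex (age–weight correlation 0.8) | 15% | 9% |
| Within-arm correlation of mg/kg with weight | −0.82 | −0.53 |

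**4. Odds ratio per 43 mg/kg when dose has no effect.** Simulated large samples, with log-odds of response falling 0.2 to 0.4 per 10 kg (assumed). With the top band to 90 kg:

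| Age–weight correlation | Planned model | Planned model, slope reversed |
|---|---|---|
| 0.6 | 1.20–1.43 | 0.70–0.82 |
| 0.75 | 1.14–1.29 | 0.77–0.88 |
| 0.85 | 1.08–1.17 | 0.83–0.92 |

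Adding continuous weight gives 0.98–1.02 throughout. With the top band ending at 70 kg, the planned model gives about 1.03–1.12 over the same slopes and correlations. A separate run, with odds ratios for response of 0.5 to 2.0 per 20 kg, gave 1.36 down to 0.72 at correlation 0.6 and 1.19 down to 0.83 at 0.8. It gave 0.99–1.01 when weight had no effect.

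**5. When dose does have an effect.** True odds ratio 1.30 per 43 mg/kg, correlation 0.75, slope 0.4 per 10 kg. If response rises with weight, the planned model returns 0.97 (1.28 with weight added). If response falls with weight, it returns 1.66 (1.31 with weight added).

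**6. Size against noise.** The standard error of the coefficient at n = 53 is about 0.61.

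- Top band to 90 kg: ln 1.08 / 0.61 = 0.13 and ln 1.43 / 0.61 = 0.59 standard errors.
- Top band to 70 kg: ln 1.03 / 0.61 = 0.05 and ln 1.12 / 0.61 = 0.19 standard errors.

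False-positive rates at a nominal 5% (top band to 90 kg): at slope −0.4 and correlation 0.75, 6.6% (n = 53) and 8.9% (n = 80), against about 5% with weight added. A second run at correlation 0.8, with weight affecting response, gave 6.1–7.9% planned against 5.7–6.1% with weight. Monte Carlo error is about ±1.3 points.

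**The case against.** The strongest reply is that the bias is conditional and the stakes are low. No passage says that response depends on weight, and without such dependence given age and sex the bias is zero. The assumed slopes are also steep. Over the 72 kg from 18 to 90 kg they imply odds ratios of exp(7.2 × 0.2) = 4.2 to exp(7.2 × 0.4) = 17.8. The model is one of several sensitivity analyses with descriptive p-values. SAP section 7.6.1 and Tables 14.2.1.2.1 and 14.2.1.2.7 already show response by arm and weight group. Most of the variance in mg/kg (78 to 90%) comes from the randomised arm, and age is a partial stand-in for weight. All of this stands and limits the point. It does not remove it: age leaves some bias even at a correlation of 0.85, and a separate summary does not change what this model estimates.

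A reader might infer more than the documents support:

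- **That this is the only planned efficacy analysis of dose in mg/kg.** It is the only one in the readable text, but the exploratory endpoints are redacted, so this cannot be verified.
- **That the model will produce or conceal a dose response.** It can, but only under a weight effect that the documents do not give.
- **That children in opposite arms receive the same mg/kg.** The ranges come close only at extreme weights (23.2 kg on low dose, 51.7; 90 kg on high dose, 53.3) and do not overlap.
- **That adding weight leaves a purely randomised contrast.** Within the bands mg/kg is not linear in weight. After adjustment it correlates about 0.95 with arm, so about 10% of its remaining variance (1 − 0.95²) is still not arm.

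**Conclusion.** The point holds as a modest, conditional weakness in one descriptive sensitivity model. That the coefficient can absorb body size follows from the dosing table and the covariate list. How much it absorbs does not follow from the documents. It rests on an assumed weight effect, an assumed age–weight correlation and an assumed spread of weights in the heaviest band, and this last assumption alone moves the upper end of the null odds ratio from about 1.12 to about 1.43. Any shift is well under one standard error at n = 53, and the avoidable excess in false positives is at most a few percentage points. The primary comparisons in SAP section 5.8.1 do not use mg/kg and are not called into question. The change is still worth making, because the model's stated purpose is to estimate a mg/kg effect and one term removes most of the dependence on an unverified condition.

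**What to change.** Add body weight as a continuous covariate to the section 7.7.1 logistic model in both phases. State that the same weight is used for mg/kg and for the covariate, namely the one that set the dose for that phase: Visit 2 for the Double-blind Acute Phase and for direct entrants to Maintenance; Visit 3.2 or 4.2 for children re-randomised from an acute phase. Also state whether mg/kg uses the assigned or the average taken dose, since the SAP specifies neither.

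Weight group would not do as well. In the scenario with slope −0.4, correlation 0.75 and top-band weights to 90 kg, it leaves a null odds ratio of 1.20, because the heaviest band is wide. With continuous weight, the coefficient rests mainly, though not entirely, on the randomised contrast, and the report should describe it that way.

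The cost is one term in a planned model, using data already collected. The standard error of the dose coefficient rises by about 5 to 8% (for example 0.61 to 0.65 at n = 53 and 0.50 to 0.53 at n = 80).

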8. DATA HANDLING CONVENTIONS

8.1 General Data Reporting Conventions

Continuous variables will be summarized using the following descriptive statistics: n, mean, median, standard deviation, Q1, Q3, minimum, maximum. Categorical and count variables will be summarized by the number of subjects (n) and the percent of subjects in each category.

See TFLs4Shire for rules on the number of decimal places to present data and p-values.

8.2 Derived Efficacy Endpoints

- Stool frequency and rectal bleeding score:
 - For both stool frequency and rectal bleeding, the symptom score (collected via the electronic diary [e-diary]) is defined as the average of the scores from the last available 3 days from the 5 days immediately prior to the visit (days -1 to -5). If there are fewer than 3 days of data available during days -1 to -5, the average will be calculated from any available days within the period. If there are no available days during the period, then the symptom score will be missing for that visit. Data collected on days when bowel preparations have been administered or when endoscopy has been performed will be excluded.
 - For stool frequency and rectal bleeding, the symptom score will be grouped into a category (0, >0 - <1, 1 - <2, 2 - <3, and 3).
- Partial UC-DAI score:
 - Sum of rectal bleeding score, stool frequency score and PGA score
- Full UC-DAI score:
 - Sum of rectal bleeding score, stool frequency score, PGA score and endoscopy score
- Clinical response: partial UC-DAI ≤ 1 (rectal bleeding=0 and stool frequency ≤ 1 and PGA=0)
- Clinical and endoscopic response: UC-DAI ≤ 2 with rectal bleeding=0 and stool frequency ≤ 1 and PGA=0, and mucosal healing (endoscopy score ≤ 1) based on central reading
- Week 8 responder status is defined based on clinical response: entered Maintenance Phase directly, responder at Week 8 of the Double-blind Acute Phase, or responder at Week 8 of the Open-label Acute Phase.

